Appendix C – EXACT Scoring Instructions

1. Computing EXACT Daily Scores

Raw Scores

Raw scores are assigned to each item response option, as shown in [Table 1](#) of this Appendix. Note that items 3, 8, 9, 10, 11, and 14 have unique scoring instructions. Item responses should be converted to item-level scores as the first step in scoring.

The recommended programming for the electronic EXACT diary does not allow a study patient to skip individual items. If a patient tries to skip a question, a message should appear to prompt the patient to complete the question. Thus, no missing data are expected for individual items in the electronic data capture setting. If missing values do occur for individual items, the scores for that day cannot be calculated and should be set to missing.

EXACT Total Score

An EXACT Total score should be computed for each day of diary collection. The EXACT Total score is based on a logit scoring system with conversion to a 0 to 100 scale for ease of interpretation and use. The scores are computed using a simple conversion table, by hand or electronically (e.g., software data interface for ePRO devices or statistical software, such as SAS®). To compute the EXACT Total score:

Convert each original item response code to an item-level raw score, by matching the responses to [Table 1](#) below. For example, for question 1, if the data-collection form or system encodes the response of “Not at all” as code 1, recode it to a zero (0) to match [Table 1](#), question 1. Note that some questions group certain original item response codes into a single item-level raw score; for example, question 3 groups original responses of “A little” and “Some” into the item-level raw score of 1.

Sum the item-level raw scores of the 14 EXACT items to form the raw summed score.

Note: do not sum the original item responses; sum the recoded values obtained in the step described above.

For each raw summed score, look up the corresponding EXACT Total score from [Table 2](#) of this appendix. The EXACT Total score ranges from 0 to 100. Sample SAS program code for converting raw summed scores to the EXACT Total score is provided in [Table 4](#) of this appendix.

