If the EXACT Total score is 0, change it to missing. This scoring rule is based on previous validation work demonstrating that moderate-to-severe COPD patients will experience symptom(s) each day, and a score of zero on all 14 EXACT items is likely to represent a situation where in order to complete the diary quickly, the respondent did not accurately report their daily symptom(s).

Where no diary entry exists for a given day, create a record in the data file for that day and enter a missing value for the EXACT Total score. Each day a patient is followed in the study must have a record for the day, even if there is no data and the EXACT Total score is missing.

Domain Scores

Three respiratory symptom domains are also embedded within the EXACT measure: Breathlessness, Cough & Sputum, and Chest Symptoms.

To compute domain scores:

Item assignments to domains are as follows. Please note that items 4, 12, 13, and 14 do not correspond to a domain score and are not used in domain-specific analyses.

- Breathlessness – Items 7, 8, 9, 10, and 11
- Cough & Sputum – Items 2 and 3
- Chest Symptoms – Items 1, 5, and 6.

For each day, sum the item-level raw scores of the items comprising the domain to form the domain raw summed score. If no diary entry exists for a given day, leave the domain raw summed score missing.

Each domain raw summed score has its corresponding “EXACT Domain” score. For each domain raw summed score, look up the corresponding EXACT domain score from [Table 3](#) below. If no diary entry exists for a given day, leave the EXACT domain score missing.

If the daily EXACT domain score is 0, change it to missing. This scoring rule is based on previous validation work demonstrating that moderate to severe COPD patients will experience symptom(s) each day, and a score of zero on all 14 EXACT items is likely to represent a situation where in order to complete the diary quickly, the respondent did not accurately report their daily symptom(s).

2. Computing Event Frequency, Duration, and Severity

All exacerbation parameters are based on the EXACT Total score.

Baseline EXACT Total Score

For studies enrolling patients during a stable baseline period, baseline EXACT values are computed and used to identify the onset of EXACT events.

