time period. Persistent Worsening is defined as an EXACT exacerbation that never meets the Recovery criteria, i.e., the patient's EXACT scores never meet the Recovery definition. All analyses including Recovery should be based on resolved events only, unless otherwise specified.

New Event (Stabilisation Phase)

Score increases consistent with Onset and occurring any time after the 7th day of the Recovery period are counted as a new event. To identify a new exacerbation, use the last available Baseline value. The reset Baseline value ($\text{Baseline}_{\text{RX}}$) is used if a patient's Baseline was re-established prior to the EXACT exacerbation; otherwise the original Baseline value from Stabilisation Phase (i.e. mean EXACT score during the first 7 days of the Stabilisation Phase (Week 3; Days 15-21)) is used. If no new event is experienced during the 4 week period post-Recovery, Baseline is reset in the manner described previously. There may be a new event beginning on the day after the day of recovery, but not on the day of recovery.

Duration (Stabilisation Phase)

Duration is the length of time in days from Onset to Recovery. Duration is calculated as the difference, in days, between the day of Onset (Day_1) and the day of Recovery (Day_R). The day of Recovery (Day_R) is not included in calculating Duration days.

Event Severity (Stabilisation Phase)

Severity is the highest EXACT Total score of the observation period from Onset (Day_1) to Recovery (Day_R), not using the 3-day Rolling Average. For patients who do not recover severity is the highest EXACT Total score of the observation period.

Table 1: Annotated EXACT for Raw Score Assignment

The following annotates the raw item-level score values associated with each text response for the EXACT items.

1. Did your chest feel congested today?	0. Not at all
	1. Slightly
	2. Moderately
	3. Severely
	4. Extremely
2. How often did you cough today?	0. Not at all
	1. Rarely
	2. Occasionally
	3. Frequently
	4. Almost constantly
3. How much mucus (phlegm) did you bring up when coughing today?	0. None at all
	1. A little
	1. Some
	2. A great deal
	3. A very great deal
NOTE: Score "A little" and "Some" the same.	
4. How difficult was it to bring up mucus (phlegm) today?	0. Not at all
	1. Slightly
	2. Moderately
	3. Quite a bit
	4. Extremely
5. Did you have chest discomfort today?	0. Not at all
	1. Slight
	2. Moderate
	3. Severe
	4. Extreme
6. Did your chest feel tight today?	0. Not at all
	1. Slightly

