	2. Moderately
	3. Severely
	4. Extremely

7. Were you breathless today?	0. Not at all 1. Slightly 2. Moderately 3. Severely 4. Extremely
8. Describe how breathless you were today:	0. Unaware of breathlessness 1. Breathless during strenuous activity 2. Breathless during light activity 3. Breathless when washing or dressing 3. Present when resting NOTE: Score "Breathless when washing or dressing" and "Present when resting" the same.
9. Were you short of breath today when performing your usual personal care activities like washing or dressing?	0. Not at all 1. Slightly 2. Moderately 3. Severely 3. Extremely 4. Too breathless to do these NOTE: Score "Severely" and "Extremely" the same.
10. Were you short of breath today when performing your usual indoor activities like cleaning or household work?	0. Not at all 1. Slightly 2. Moderately 3. Severely 3. Extremely 3. Too breathless to do these NOTE: Score "Severely," "Extremely," and "Too breathless to do these" the same.
11. Were you short of breath today when performing your usual activities outside the home such as yard work or errands?	0. Not at all 1. Slightly 2. Moderately 3. Severely 3. Extremely 3. Too breathless to do these NOTE: Score "Severely," "Extremely," and "Too breathless to do these" the same.

12. Were you tired or weak today?	0. Not at all 1. Slightly 2. Moderately 3. Severely 4. Extremely
13. Last night, was your sleep disturbed?	0. Not at all 1. Slightly 2. Moderately 3. Severely 4. Extremely
14. How scared or worried were you about your lung problems today?	0. Not at all 1. Slightly 2. Moderately 3. Severely 3. Extremely NOTE: Score "Severely" and "Extremely" the same.

Table 2: Raw Summed Score to Scale Score Conversion Table for EXACT Total Score

Raw Summed Score	EXACT® Total Score	Raw Summed Score (continued)	EXACT® Total Score
0	0	26	50
1	8	27	51
2	13	28	52
3	17	29	53
4	20	30	54
5	23	31	55
6	25	32	57
7	27	33	58
8	28	34	59
9	30	35	60
10	31	36	61
11	33	37	63
12	34	38	64
13	36	39	65
14	37	40	67
15	38	41	68
16	39	42	70
17	40	43	72
18	41	44	73
19	42	45	75
20	43	46	77
21	44	47	80
22	46	48	83
23	47	49	87
24	48	50	92
25	49	51	100

This conversion table converts raw summed scores to a 0 to 100 scale, for ease of interpretation.

Table 3: Raw Summed Score to Scale Score Conversion Table for EXACT Domains

Domain Raw Summed Score ^a	Breathlessness Domain Score	Cough & Sputum Domain Score	Chest Symptoms Domain Score
0	0	0	0
1	11	13	12
2	19	25	23
3	25	39	31
4	30	56	38

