5	34	72	45
6	38	86	52
7	42	100	58
8	45		65
9	48		72
10	52		79
11	56		88
12	60		100
13	65		
14	71		
15	78		
16	87		
17	100		

^aThe maximum score for the chest symptoms domain is 12. The maximum score for the Cough & Sputum domain is 7.

Table 4: SAS Coding Instructions for Computing Daily Scores

The following example assumes all original item responses are coded as 0, 1, 2, 3, 4, etc. on the data collection forms or electronic data capture system, ordered from least severe to most severe. In this case, only items 3, 8, 9, 10, 11, and 14 need to be recoded to form item-level scores. If the original codes begin with 1 for least severe (e.g., 1, 2, 3, 4, 5 for question 1), then the codes must be shifted to a 0 starting point for all items before these SAS statements can be used.

1. Assign raw score values associated with each response category for the EXACT® items:
	<pre> if q3 in (1,2) then q3=1; else if q3 in (3) then q3=2; else if q3 in (4) then q3=3; if q8 in (3,4) then q8=3; if q9 in (3,4) then q9=3; else if q9 in (5) then q9=4; if q10 in (3,4,5) then q10=3; if q11 in (3,4,5) then q11=3; if q14 in (3,4) then q14=3; rawsum=sum (of q1-q14); breathlesssum=sum (of q7-q11); coughsum=sum (of q2 q3); chestsum=sum (of q1 q5 q8); </pre>

2. Assign the EXACT® Total score for each raw summed score:
	<pre> select (rawsum); when(0) Exact_total=0; when(1) Exact_total=8; when(2) Exact_total=13; when(3) Exact_total=17; when(4) Exact_total=20; when(5) Exact_total=23; when(6) Exact_total=25; when(7) Exact_total=27; when(8) Exact_total=28; when(9) Exact_total=30; when(10) Exact_total=31; when(11) Exact_total=33; when(12) Exact_total=34; when(13) Exact_total=36; when(14) Exact_total=37; when(15) Exact_total=38; when(16) Exact_total=39; when(17) Exact_total=40; when(18) Exact_total=41; when(19) Exact_total=42; when(20) Exact_total=43; when(21) Exact_total=44; when(22) Exact_total=46; when(23) Exact_total=47; when(24) Exact_total=48; when(25) Exact_total=49; when(26) Exact_total=50; when(27) Exact_total=51; when(28) Exact_total=52; </pre>

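### The sample SAS code in SAP Appendix C sums items 1, 5 and 8 for the EXACT Chest Symptoms domain, where the scoring text requires items 1, 5 and 6

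*SAP*

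**What the plan says.** SAP Appendix C, under Domain Scores, assigns items to domains: "Chest Symptoms – Items 1, 5, and 6" and "Breathlessness – Items 7, 8, 9, 10, and 11". Table 1 of the appendix gives the item content. Item 6 is "6. Did your chest feel tight today", with responses scored 0 to 4. Item 8 is "8. Describe how breathless you were today", scored 0 to 3 because its two worst responses share the value 3. The footnote to Table 3 puts the maximum raw Chest Symptoms score at 12, and the table converts 12 to a domain score of 100.

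The code in Table 4 forms the raw sums with "rawsum=sum (of q1-q14", "breathlesssum=sum (of q7-q11" and "chestsum=sum (of q1 q5 q8". The Breathlessness line matches the text. The Chest Symptoms line does not.

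On missing items, the appendix says under Raw Scores: "If missing values do occur for individual items, the scores for that day cannot be calculated and should be set to missing". Just before that it explains that the recommended electronic diary does not let a patient skip an item, so item-level gaps are not expected.

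**The concern.** One of the three items in the coded chest score is a breathlessness item, and the domain's own tightness item is left out. A program built from that line would run the chest sum without any error message, so the fault would not announce itself.

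The domain scores are used. SAP Section 8.6.3.7 applies an MMRM to each of the three subscores, Section 8.6.3.9 applies ANCOVA to their AUCs, and Section 8.6.3.10 summarises their change from baseline. With item 8 in two domains, a treatment effect on breathlessness would carry over into the chest domain and could look like a second, separate effect. An effect on chest tightness would appear in no domain.

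The second, smaller question is whether the code respects the missing-item rule. SAS SUM adds whatever arguments are present and returns missing only when all are missing. A partly completed diary would therefore be scored, and scored low if a skipped item's true value is above 0.

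**Working it through.** **Inputs.** Item maxima from Appendix C Table 1: items 3, 8, 10, 11 and 14 have maximum 3 and the other nine have maximum 4. Conversions come from Appendix C Tables 2 and 3.

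**Reproducing the plan's own maxima.**
- Total: 9 × 4 + 5 × 3 = 51, the last row of Table 2.
- Breathlessness, items 7 to 11: 4 + 3 + 4 + 3 + 3 = 17, as in Table 3.
- Cough & Sputum, items 2 and 3: 4 + 3 = 7, as in Table 3.
- Chest Symptoms, items 1, 5 and 6: 4 + 4 + 4 = 12, as in Table 3.

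All four agree with the written item assignments.

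**The code as printed.** Items 1, 5 and 8 give 4 + 4 + 3 = 11. Table 3 converts 11 to 88, so the row for 12 (score 100) cannot be reached.

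**How often the two versions differ.** Items 1, 5 and 6 take five values each and item 8 takes four, giving 5 × 5 × 5 × 4 = 500 response patterns. The conversion is strictly increasing, so the two scores agree only when item 6 equals item 8: 5 × 5 × 4 = 100 patterns, or 20%. This counts patterns without weighting them by how often patients give them, so it is not a forecast of the share of patient-days affected.

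**Size of the difference (code minus text).**
- From the conversion table alone the range is −38 to +31. The lower end is item 6 = 4 with items 1, 5 and 8 at 0 (0 against 38). The upper end is item 8 = 3 with items 1, 5 and 6 at 0 (31 against 0).
- Appendix C then recodes a domain score of 0 to missing, so in those two cases a day is lost or wrongly gained. This happens in 4 patterns (lost) and 3 patterns (gained).
- Among the 492 patterns that both versions score, the range is −35 to +26. The lower end is items 1, 5 and 6 at 4 and item 8 at 0 (raw 8 against 12: 65 − 100). The upper end is item 1 at 1, items 5 and 6 at 0 and item 8 at 3 (raw 4 against 1: 38 − 12).

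**Missing items under SUM.** With all 14 items at 2, the raw sum is 28 and the Total is 52.

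| Items missing | Raw sum | Total from code | Total under the written rule |
|---|---|---|---|
| 1 | 26 | 50 | missing |
| 2 | 24 | 48 | missing |
| 3 | 22 | 46 | missing |
| 4 | 20 | 43 | missing |

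For the chest domain, three items at 2 score 52 (raw 6). With one missing, the code gives 38 (raw 4).

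**The case against.** **The code is illustrative and incomplete.** Appendix C introduces it as sample code. As supplied, it cannot run unaltered: step 1 creates `breathlesssum` and `coughsum`, but the later lookups select on `breathlessnessum` and `coughsputum`, and no lookup block is closed with an END. It also omits the recoding of 0 to missing. A programmer has to rebuild it, and the written item list is explicit. This stands, and a reader should not infer that the trial's chest scores were or will be computed wrongly. The documents do not show the production program. It does not remove the point, because Table 4 is headed as coding instructions, Section 7.1.4.7 refers to Appendix C for scoring, and the chest variable name does match between the sum and its lookup.

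**The 8 may be a reading error for 6.** The text was machine-read from a PDF and the part on item 8 rests on one digit. This cannot be settled from the text, so the original page comes first. If it shows q6, that part falls.

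**The consequence is narrow.** This stands. Appendix C bases all exacerbation parameters on the Total score, which does not use the chest sum. The listed secondary endpoint that names domain scores (SAP Section 4.2, item 12) is only summarised descriptively, and Protocol Section 13.5.1 treats all analyses as exploratory.

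**Partly missing diaries are not expected.** This largely stands, and the written rule already covers the case. However, the skip block is described as recommended programming, and Protocol Section 17.1 allows EXACT-PRO to be entered directly in the eCRF, so the block is not shown to apply everywhere. A reader might also take the 9-point fall with four missing items (52 to 43) as a false improvement event. It equals the threshold in size, but improvement is judged on a rolling average against the previous day's maximum observed value, so one such day need not trigger it.

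**Conclusion.** On the text as supplied, the chest line in Table 4 is wrong. It contradicts the written item assignment, the item content in Table 1 and the maximum in Table 3, all of which require items 1, 5 and 6. Used as printed, it would cap the domain at 88, change the score in 400 of 500 unweighted response patterns, and blur the separation between the chest and breathlessness domains in secondary analyses. It would not alter the EXACT Total score, onset, improvement, recovery, duration or severity, or the FEV1 primary endpoint.

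The missing-item conflict is real but minor. It can touch the Total and all three domains, but only on days with some items missing, which the SAP does not expect. A wholly missing diary still gives a missing sum.

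The conclusion assumes that the printed digit is truly 8 and that the line, or a copy of it, could reach the production program. The behaviour of SUM is a property of SAS and is not stated in the documents.

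**What to change.** 1. Check the digit on the original page of SAP Appendix C, Table 4.
2. If it is an 8, change the line to `chestsum=sum(of q1 q5 q6);`.
3. Confirm that the production scoring program uses items 1, 5 and 6, whatever the appendix prints.
4. Compute the total and all three domain sums only when `nmiss(of q1-q14)=0`, and otherwise set all of that day's scores to missing. Checking each domain's own items would not be enough: it would still give a chest score on a day when item 9 is missing, while the written rule blanks every score for that day.
5. While the block is open, align the mismatched variable names, close the lookup blocks, and give the three domain lookups a branch for missing sums, as the Total lookup already has.

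The cost is one corrected line, one condition around four sums and a short program check. No new data are needed and no analysis model changes.

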Appendix D – Chronic Respiratory Questionnaire (CRQ)

[READ TO RESPONDENT]

i. This questionnaire is designed to find out how you have been feeling during the last 2 weeks.

ii. In the first section, you will be asked to answer questions about activities, which make some people feel short of breath. In the next section, you will be asked about your mood and how you have been feeling.

iii. Remember, there are no right or wrong answers.

iv. I would now like you to describe how much shortness of breath you have experienced during the last 2 weeks while doing activities, which make some people feel short of breath. When you are answering the questions about how short of breath you have been, please indicate if you have not done an activity during the last two weeks.

[FOR ALL SUBSEQUENT QUESTIONS, ENSURE THE RESPONDENT HAS THE APPROPRIATE RESPONSE CARD IN FRONT OF THEM BEFORE STARTING QUESTION]

1. Please indicate how much shortness of breath you have had during the last 2 weeks while feeling emotional such as angry or upset by choosing one of the following options from the card in front of you. [GREEN CARD]
	
EXTREMELY SHORT OF BREATH 
 
VERY SHORT OF BREATH 
 
QUITE A BIT SHORT OF BREATH 
 
MODERATE SHORTNESS OF BREATH 
 
SOME SHORTNESS OF BREATH 
 
A LITTLE SHORTNESS OF BREATH 
 
NOT AT ALL SHORT OF BREATH 
 
NOT DONE 

2. Please indicate how much shortness of breath you have had during the last 2 weeks while taking care of your basic needs (such as bathing, showering, eating or dressing) by choosing one of the following options from the card in front of you. [GREEN CARD]
	
EXTREMELY SHORT OF BREATH 
 
VERY SHORT OF BREATH 
 
QUITE A BIT SHORT OF BREATH 
 
MODERATE SHORTNESS OF BREATH 
 
SOME SHORTNESS OF BREATH 
 
A LITTLE SHORTNESS OF BREATH 
 
NOT AT ALL SHORT OF BREATH 
 
NOT DONE 


3. Please indicate how much shortness of breath you have had during the last 2 weeks while walking by choosing one of the following options from the card in front of you. [GREEN CARD]
	
EXTREMELY SHORT OF BREATH 
 
VERY SHORT OF BREATH 
 
QUITE A BIT SHORT OF BREATH 
 
MODERATE SHORTNESS OF BREATH 
 
SOME SHORTNESS OF BREATH 
 
A LITTLE SHORTNESS OF BREATH 
 
NOT AT ALL SHORT OF BREATH 
 
NOT DONE 

4. Please indicate how much shortness of breath you have had during the last 2 weeks while performing chores (such as housework, shopping, groceries) by choosing one of the following options from the card in front of you. [GREEN CARD]
	
EXTREMELY SHORT OF BREATH 
 
VERY SHORT OF BREATH 
 
QUITE A BIT SHORT OF BREATH 
 
MODERATE SHORTNESS OF BREATH 
 
SOME SHORTNESS OF BREATH 
 
A LITTLE SHORTNESS OF BREATH 
 
NOT AT ALL SHORT OF BREATH 
 
NOT DONE 

5. Please indicate how much shortness of breath you have had during the last 2 weeks while participating in social activities by choosing one of the following options from the card in front of you. [GREEN CARD]
	
EXTREMELY SHORT OF BREATH 
 
VERY SHORT OF BREATH 
 
QUITE A BIT SHORT OF BREATH 
 
MODERATE SHORTNESS OF BREATH 
 
SOME SHORTNESS OF BREATH 
 
A LITTLE SHORTNESS OF BREATH 
 
NOT AT ALL SHORT OF BREATH 
 
NOT DONE 


6. In general, how much of the time during the last 2 weeks have you felt frustrated or impatient? Please indicate how much of the time you have felt frustrated or impatient by choosing one of the following options from the card in front of you. [BLUE CARD]
	
ALL OF THE TIME 
 
MOST OF THE TIME 
 
A GOOD BIT OF THE TIME 
 
SOME OF THE TIME 
 
A LITTLE OF THE TIME 
 
HARDLY ANY OF THE TIME 
 
NONE OF THE TIME 

7. How often during the last 2 weeks did you have a feeling of fear or panic when you had difficulty getting your breath? Please indicate how often you had a feeling of fear or panic when you had difficulty getting your breath by choosing one of the following options from the card in front of you. [BLUE CARD]
	
ALL OF THE TIME 
 
MOST OF THE TIME 
 
A GOOD BIT OF THE TIME 
 
SOME OF THE TIME 
 
A LITTLE OF THE TIME 
 
HARDLY ANY OF THE TIME 
 
NONE OF THE TIME 

8. What about fatigue? How tired have you felt over the last 2 weeks? Please indicate how tired you have felt over the last 2 weeks by choosing one of the following options from the card in front of you. [ORANGE CARD]
	
EXTREMELY TIRED 
 
VERY TIRED 
 
QUITE A BIT OF TIREDNESS 
 
MODERATELY TIRED 
 
SOMEWHAT TIRED 
 
A LITTLE TIRED 
 
NOT AT ALL TIRED 

9. How often during the last 2 weeks have you felt embarrassed by your coughing or heavy breathing? Please indicate how much of the time you felt embarrassed by your coughing or heavy breathing by choosing one of the following options from the card in front of you. [BLUE CARD]
	
ALL OF THE TIME 
 
MOST OF THE TIME 
 
A GOOD BIT OF THE TIME 
 
SOME OF THE TIME 
 
A LITTLE OF THE TIME 
 
HARDLY ANY OF THE TIME 
 
NONE OF THE TIME 


10. In the last 2 weeks, how much of the time did you feel very confident and sure that you could deal with your illness? Please indicate how much of the time you felt very confident and sure that you could deal with your illness by choosing one of the following options from the card in front of you. [YELLOW CARD]
	
NONE OF THE TIME 
 
A LITTLE OF THE TIME 
 
SOME OF THE TIME 
 
A GOOD BIT OF THE TIME 
 
MOST OF THE TIME 
 
ALMOST ALL OF THE TIME 
 
ALL OF THE TIME 

11. How much energy have you had in the last 2 weeks? Please indicate how much energy you have had by choosing one of the following options from the card in front of you. [PINK CARD]
	
NO ENERGY 
 
A LITTLE ENERGY 
 
SOME ENERGY 
 
MODERATELY ENERGETIC 
 
QUITE A BIT OF ENERGY 
 
VERY ENERGETIC 
 
FULL OF ENERGY 

12. In general, how much of the time did you feel upset, worried or depressed during the last 2 weeks? Please indicate how much of the time you felt upset, worried or depressed during the past 2 weeks by choosing one of the following options from the card in front of you. [BLUE CARD]
	
ALL OF THE TIME 
 
MOST OF THE TIME 
 
A GOOD BIT OF THE TIME 
 
SOME OF THE TIME 
 
A LITTLE OF THE TIME 
 
HARDLY ANY OF THE TIME 
 
NONE OF THE TIME 

13. How often during the last 2 weeks did you feel you had complete control of your breathing problems? Please indicate how often you felt you had complete control of your breathing problems by choosing one of the following options from the card in front of you. [YELLOW CARD]
	
NONE OF THE TIME 
 
A LITTLE OF THE TIME 
 
SOME OF THE TIME 
 
A GOOD BIT OF THE TIME 
 
MOST OF THE TIME 
 
ALMOST ALL OF THE TIME 
 
ALL OF THE TIME 


14. How much of the time during the last 2 weeks did you feel relaxed and free of tension? Please indicate how much of the time you felt relaxed and free of tension by choosing one of the following options from the card in front of you. [YELLOW CARD]
	
NONE OF THE TIME 
 
A LITTLE OF THE TIME 
 
SOME OF THE TIME 
 
A GOOD BIT OF THE TIME 
 
MOST OF THE TIME 
 
ALMOST ALL OF THE TIME 
 
ALL OF THE TIME 

15. How often during the last 2 weeks have you felt low in energy? Please indicate how often during the last 2 weeks you felt low in energy by choosing one of the following options from the card in front of you. [BLUE CARD]
	
ALL OF THE TIME 
 
MOST OF THE TIME 
 
A GOOD BIT OF THE TIME 
 
SOME OF THE TIME 
 
A LITTLE OF THE TIME 
 
HARDLY ANY OF THE TIME 
 
NONE OF THE TIME 

16. In general, how often during the last 2 weeks have you felt discouraged or down in the dumps? Please indicate how often during the last 2 weeks you felt discouraged or down in the dumps by choosing one of the following options from the card in front of you. [BLUE CARD]
	
ALL OF THE TIME 
 
MOST OF THE TIME 
 
A GOOD BIT OF THE TIME 
 
SOME OF THE TIME 
 
A LITTLE OF THE TIME 
 
HARDLY ANY OF THE TIME 
 
NONE OF THE TIME 

17. How often during the last 2 weeks have you felt worn out or sluggish? Please indicate how much of the time you felt worn out or sluggish by choosing one of the following options from the card in front of you. [BLUE CARD]

ALL OF THE TIME

MOST OF THE TIME

A GOOD BIT OF THE TIME

SOME OF THE TIME

A LITTLE OF THE TIME

HARDLY ANY OF THE TIME

NONE OF THE TIME

18. How happy, satisfied, or pleased have you been with your personal life during the last 2 weeks? Please indicate how happy, satisfied or pleased you have been by choosing one of the following options from the card in front of you. [GREY CARD]

VERY DISSATISFIED, UNHAPPY

MOST OF THE TIME

GENERALLY DISSATISFIED, UNHAPPY

SOMEWHAT DISSATISFIED, UNHAPPY

GENERALLY SATISFIED, PLEASED

HAPPY MOST OF THE TIME

VERY HAPPY MOST OF THE TIME

EXTREMELY HAPPY, COULD NOT BE MORE SATISFIED OR PLEASED

19. How often during the last 2 weeks did you feel upset or scared when you had difficulty getting your breath? Please indicate how often during the past 2 weeks you felt upset or scared when you had difficulty getting your breath by choosing one of the following options from the card in front of you. [BLUE CARD]

ALL OF THE TIME

MOST OF THE TIME

A GOOD BIT OF THE TIME

SOME OF THE TIME

A LITTLE OF THE TIME

HARDLY ANY OF THE TIME

NONE OF THE TIME

20. In general, how often during the last 2 weeks have you felt restless, tense or uptight? Please indicate how often you felt restless tense, or uptight by choosing one of the following options from the card in front of you. [BLUE CARD]

ALL OF THE TIME

MOST OF THE TIME

A GOOD BIT OF THE TIME

SOME OF THE TIME

A LITTLE OF THE TIME

HARDLY ANY OF THE TIME

NONE OF THE TIME

